1.2 Study Rationale

The purpose of this project is to expand access to trauma-focused treatment among Medicaid Enrollees with PTSD, thereby improving the quality of mental health services delivered to this population. This project directly addresses the Michigan Department of Health and Human Services (MDHHS) Mental Health and Wellness commission priority to provide “better access to high quality, coordinated and consistent service and care between agencies, service providers and across geographical boundaries.”

The project goals are to evaluate the delivery and sustainability of a brief trauma-focused treatment, Prolonged Exposure for Primary Care (PE-PC), an evidence-based intervention for PTSD, when delivered via telehealth to patients enrolled at CHCs in Michigan. CHCs serve 680,000 Michigan residents across 260 delivery sites. Ninety-two percent of CHC patients have incomes below 200 percent of the federal poverty level. Approximately 16 percent of CHC patients are uninsured, and more than half rely on Medicaid for their insurance. Thus, providing PTSD treatment to CHC patients will improve care to Medicaid enrollees and promote Mental Health and Wellness commission priorities of developing a trauma informed system that includes implementation of evidence-based trauma-informed care.

To address the high burden of PTSD in Medicaid enrollees in Michigan CHCs, we plan to deliver PE-PC to patients in CHCs. This treatment consists of four 30-minute sessions of in-vivo and narrative exposure, with content drawn from the PE model.¹ Recently published efficacy data from a randomized controlled trial showed that PE-PC significantly reduced PTSD and depression symptoms as compared to usual primary care treatment.¹⁰ These changes were maintained at 6-month follow-up.

2 OUTCOMES

2.1 Primary Outcome

The Primary Outcome measure is change in PTSD symptoms as measured by the PTSD Checklist for DSM-5 (PCL-5). PCL-5 will be administered at baseline, 2-months post-enrollment (around the time of treatment completion) and 4-months post- enrollment. Two 2-month and 4-month surveys will be administered regardless of whether the patient has completed the intervention.

1. PCL-5 [Time Frame: Baseline, 2-months, 4-months]

The PCL-5¹¹ is a 20-item self-report measure designed to assess PTSD symptoms as defined by the DSM-5. Each item of the PCL-5 is scored on a five point scale ranging from 0 ("not at all") to 4 ("extremely"). The PCL-5 has strong internal consistency, test-retest reliability, and convergent and discriminant validity.^{12,13} Scores ≥ 33 indicate a probable diagnosis of PTSD.

2.2 Secondary Outcomes

1. Depressive symptoms (measured by the Patient Health Questionnaire; PHQ-9)^{14,15} [Time Frame: Baseline, 2-months, 4-months]
2. Recovery goals (measured by the Recovery Assessment Scale; RAS)^{16,17} [Time Frame: Baseline, 2-months, 4-months]
3. Posttraumatic cognitions (measured by the Post-Traumatic Cognitions Inventory; PTCI)¹⁸ [Time Frame: Baseline, 2-months, 4-months]

3 STUDY DESIGN

The goal of this pilot project is to deliver PE-PC to 50 patients via telehealth and evaluate patients' engagement with the treatment, satisfaction, and PTSD-related outcomes. This is an open trial. All participants will receive the same intervention.

4 SELECTION AND ENROLLMENT OF PARTICIPANTS

The population of interest is individuals with PTSD who receive services from CHCs in Michigan.

4.1 Inclusion Criteria

The goal of the study inclusion and exclusion criteria is to identify a broadly representative sample of CHC patients with PTSD.

Patients will be eligible for the study if they:

- 1) are age 18 years or older
- 2) receive care at a Michigan CHC
- 3) have a PCL-5 score ≥ 33
- 4) have had psychotropic medication stability for at least 4 weeks

4.2 Exclusion Criteria

Patients will be excluded if they are: 1) substantially cognitively impaired, 2) unable to agree to study procedures for any reason (including incompetency), 3) at high risk of suicide, or 4) currently engaged in a trauma-focused behavioral treatment (such as Prolonged Exposure or Cognitive Processing Therapy). Patients who do not speak English will be excluded for logistical reasons.

4.3 Recruitment

Participants will be recruited from the following CHCs: Family Medical Center of Michigan, Hamilton Community Health Network, and Family Health Care. All three clinics are all currently engaged in University of Michigan research studies and strongly endorse the current study.

5 STUDY INTERVENTIONS

5.1 Delivery and Duration

PE-PC will be delivered by the telepsychologist via interactive video technology, or telehealth.

5.2 Interventionist Training

Therapist training and PE-PC implementation PE-PC will be guided by [name] and [name], treatment developers of PE-PC. [name] and [name] have established a PE-PC training protocol that includes didactic training followed by phone consultation on training cases. Trainers will augment this training with case review to establish competence.

5.3 Delivery of Treatment

Eligible participants are individuals presenting in CHCs who screen positive for PTSD, using validated screening measures currently used in multiple Michigan CHCs. Those who screen positive will be connected by a warm handoff to the research assistant (or will call us after being provided with our contact information), who will review inclusion/exclusion criteria, present the study information sheet, and schedule the first meeting with the telepsychologist.

PE-PC treatment will follow the PE-PC manual and patient workbook. Treatment content for PE-PC is drawn from the PE model and condensed so as to deliver the most efficacious components of PE. PE-PC consists of four, 30-minute appointments scheduled approximately once a week over 4-6 weeks (to accommodate scheduling and missed appointments). Before beginning the 4-session treatment, the telepsychologist will schedule an initial appointment with the patient to determine the index trauma and answer any questions about the treatment. During the first PE-PC session, the PC-MHI provider will review the “Confronting Uncomfortable Memories” activity workbook to be completed at home and brought back for use in subsequent sessions. The workbook asks the patient to write a detailed first-person narrative of the event associated with the greatest level of current distress, including recollection of personal thoughts, feelings, and physical reactions. Emotional processing questions are also included. In addition, the telepsychologist will plan for in-vivo exposure activities between sessions. The patient will be instructed to complete the memory exposure for 30 minutes each day between sessions. At the second PE-PC session, the telepsychologist will review the patient’s exposures, problem-solve any implementation difficulties, and process the exercises. The patient will then read the narrative and his or her answers to the emotional processing questions out loud and they will process the exercise. Practice continues between sessions. This session format and content are repeated at the third and fourth sessions. At the end of the fourth session, the telepsychologist and patient will review treatment progress assisted by results of the PTSD Checklist for DSM-5 (PCL-5) administered during the fourth session. Participants who still need or desire treatment at the conclusion of PE-PC will receive referrals to other mental health resources.

6 STATISTICAL ANALYSIS

We used paired t-tests and multiple regression to determine symptom change over time. Multiple imputation was used to impute missing data. Ten imputed datasets were generated, and coefficients and standard errors were adjusted for the variability between imputations according to Rubin’s combination rule.¹⁹ We included auxiliary variables that were correlated with the missing variables at $r > 0.4$.²⁰ Imputation procedures were conducted in SAS, using the Markov Chain Monte Carlo approach.

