**Michigan Mental Health Integration Partnership - Implementing PTSD Treatment in Federally
Qualified Health Centers for Michigan Medicaid Enrollees
PE-PC Pilot**

National Clinical Trial Number: NCT03711266

Date: September 23, 2021

Principal Investigator:

[name], Assistant Professor, University of Michigan Department of Psychiatry

Supported by:

Michigan Mental Health Integration Partnership (MIP) Scholars program
Michigan Department of Health and Human Services

PROTOCOL SUMMARY

Title:	PE-PC Pilot
Study Description:	A study to evaluate the delivery and sustainability of a brief trauma-focused treatment, Prolonged Exposure for Primary Care (PE-PC), an evidence-based intervention for PTSD, delivered via telehealth to patients in Community Health Centers (CHCs) in Michigan.
Outcomes:	
Primary Outcome: PE-PC participants will experience reductions in PTSD symptoms as measured by the PTSD Checklist for DSM-5 (PCL-5) at 2 months and 4 months.
 
Secondary Outcomes: PE-PC participants will experience reductions in depression as measured by the PHQ-9 at 2 months and 4 months. We will also examine the mechanisms of PE-PC's effect by measuring the two potential mediators of intervention effectiveness, recovery goals (Recovery Assessment Scale; RAS) and posttraumatic cognitions (Post-Traumatic Cognitions Inventory; PTCI).

Intervention Information:	Deliver PE-PC to patients via telehealth. This treatment consists of four 30-minute sessions of in-vivo and narrative exposure, with content drawn from the PE model. ¹
Study Population:	The sample will consist of 50 participants, age 18 and older, of any gender, race or ethnicity, who are currently enrolled at a CHC and screen positive for PTSD on the PCL-5 (PCL-5 \geq 33).
Locations:	University of Michigan Family Medical Center of Michigan Hamilton Community Health Network Family Health Care
Estimated Study Start Date:	October 1, 2018
Study Duration:	2 years

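### Pooling only ten imputed datasets leaves avoidable Monte Carlo noise in the PCL-5 standard error, interval and p-value; 100 with a recorded seed would remove most of it

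*Combined protocol and SAP*

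**What the plan says.** Section 6 gives the whole missing-data method. "Multiple imputation was used to impute missing data"; "Imputation procedures were conducted in SAS, using the Markov Chain Monte Carlo approach". On the number of imputations and the pooling, it says "Ten imputed datasets were generated, and coefficients and standard errors were adjusted for the variability between imputations", and it names Rubin's rule as the method of combination. Auxiliary variables correlated above 0.4 with the incomplete variables enter the imputation model. The analyses that are pooled are described thus: "We used paired t-tests and multiple regression to determine symptom change over time".

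The sample is a single group. The Protocol Summary says "The sample will consist of 50 participants", and Section 3 describes the design in these words: "This is an open trial. All participants will receive the same intervention".

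The documents do not state a random seed, an expected or observed missing-data rate, a fraction of missing information, a reason for choosing ten, the degrees of freedom used in pooling, a significance level or a confidence level.

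**The concern.** Ten imputations are often defended by the efficiency of the pooled point estimate, which is high. That is the wrong yardstick for inference. The quantity that ten draws estimate poorly is the variance between imputations, and it enters the pooled standard error, the pooled degrees of freedom and therefore the p-value.

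Two analysts who apply Section 6 to the same data with different seeds can report visibly different intervals for the primary outcome. Because no seed is given, the result cannot be reproduced exactly from the plan. In a pilot of 50 patients without a comparator, the estimated change and its precision are the main quantitative product, so noise that can be removed at no real cost should be removed.

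A secondary question is which degrees of freedom accompany the pooled standard error. With 50 participants this choice is not automatic, and the text is silent on it.

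**Working it through.** There is no figure in the plan to reproduce, because it reports no interval, power or missing-data rate.

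**Inputs.** Number of imputations m = 10 (Section 6). N = 50, one group (Protocol Summary, Section 3), so a paired t-test on complete data has 50 − 1 = 49 df; a regression has fewer. Assumed, because the documents do not give them: a two-sided 95% interval, and a share of variance due to missing data, λ, of 0.1 to 0.5.

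**Notation.** U is the mean within-imputation variance and B the between-imputation variance. The total is T = U + (1 + 1/m)B, and λ = (1 + 1/m)B/T.

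**1. Noise in the half-width.** For fixed data, the estimate of B from m draws behaves like B·χ²(m−1)/(m−1), so its coefficient of variation (CV) is √(2/(m−1)). At m = 10 this is √(2/9) = 47%; at m = 100 it is √(2/99) = 14%. To first order, the CV of the pooled standard error is ½λ√(2/(m−1)). At λ = 0.3 this gives 0.5 × 0.3 × 0.471 = 7.1% for m = 10 and 0.5 × 0.3 × 0.142 = 2.1% for m = 100. The t multiplier also moves with the estimated λ, which adds a little. Simulating the full half-width (classical df) gives:

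| λ | CV, m = 10 | CV, m = 100 |
|---|---|---|
| 0.1 | 2.5% | 0.7% |
| 0.2 | 5% | 1.4% |
| 0.3 | 8% | 2.2% |
| 0.4 | 10% | 2.9% |
| 0.5 | 13% | 3.6% |

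Small-sample df make these CVs slightly larger (4.0% at λ = 0.5, m = 100). At λ = 0.3 and m = 10, the 95th percentile of the half-width over seeds is about 1.28 times the 5th; at m = 100 the ratio is about 1.07.

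**2. Noise in the estimate.** The Monte Carlo standard error of the pooled estimate is √(B/m). Since B = λT·m/(m+1), this is √(λ/(m+1)) pooled standard errors.
- m = 10: √(0.1/11) = 0.10 to √(0.5/11) = 0.21.
- m = 100: √(0.1/101) = 0.03 to √(0.5/101) = 0.07.

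**3. Degrees of freedom, if the classical formula was used.** Classical df = (m−1)/λ² = 9/λ². This exceeds 49 when λ < √(9/49) = 0.43. The Barnard-Rubin df = 1/(1/df_classical + 1/df_obs), with df_obs = (50/52) × 49 × (1 − λ). At λ = 0.3, df_obs = 33.0 and the combined df = 1/(1/100 + 1/33.0) = 24.8.

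| λ | Classical df | Barnard-Rubin df | t multipliers | Classical smaller by |
|---|---|---|---|---|
| 0.1 | 900 | 40.5 | 1.963, 2.020 | 2.9% |
| 0.3 | 100 | 24.8 | 1.984, 2.060 | 3.7% |
| 0.5 | 36 | 14.2 | 2.028, 2.141 | 5.3% |

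A smaller multiplier does not by itself show undercoverage. Simulations of a paired change were run with n = 50, m = 10, 10% to 40% missing completely at random and baseline correlation 0.5 (all assumed). They gave two-sided error of 5.1% to 5.4% with classical df and 4.3% to 4.5% with Barnard-Rubin df. Other runs with similar inputs gave up to 6.2% for classical df and 4.1% to 5.3% for Barnard-Rubin.

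**The case against.** **Ten imputations are efficient enough.** The relative efficiency of the estimate is 1/(1 + λ/m), which is 0.99 at λ = 0.1 and 0.95 at λ = 0.5. This is true, but it concerns the point estimate only and says nothing about the stability of the standard error or p-value.

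**Every finite m depends on the seed, and 100 is a preference.** The first part is true: 100 does not remove the noise. It does cut it by a factor of three to four, as the first table shows. Fifty would achieve much of this (CV about 3.1% at λ = 0.3), so 100 is a convenient choice and not a threshold.

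**The size rests on a missing-data rate that nobody has stated.** This stands. Section 6 uses auxiliary variables, and the PCL-5 is measured at two follow-ups, so λ may be well below the raw proportion missing. If λ is near 0.1, the noise is small even with ten imputations.

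**This is an open pilot with no stated decision threshold.** This also stands, and it limits the consequence: a large change in PCL-5 would not be overturned by noise of this order.

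**A reader might infer that the intervals are systematically too narrow**, because the classical df can exceed the 49 available from complete data. The documents do not support that. Section 6 names the combination rule for coefficients and standard errors but never says which df were used, and the rule does not exclude a small-sample adjustment. Even if the classical df were used, the simulated error stays within about one point of 5%, and in several settings Barnard-Rubin is as far below 5% as the classical rule is above it.

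**Conclusion.** The point holds as one of avoidable imprecision. The plan fixes ten imputations and gives no seed, so the primary PCL-5 interval carries seed-to-seed variation in half-width with a CV of about 2.5% to 13%, against about 0.7% to 4% at 100 imputations. The corresponding movement in the estimate is 0.10 to 0.21 standard errors against 0.03 to 0.07. These figures follow from m alone once λ is assumed to be 0.1 to 0.5; they do not need an assumption about the SD of the PCL-5. There is no bias.

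The degrees-of-freedom question is minor and conditional. If the classical formula was used, the t multiplier is about 3% to 5% smaller than under Barnard-Rubin. Whether it was used cannot be read from the text, and the effect on error rates is small. Increasing m would not settle it: at λ = 0.3 the multiplier gap is still 3.7% with 50 imputations. The two matters need separate remedies.

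**What to change.** - In Section 6, change ten imputed datasets to 100, and record the random seed.
- Report the fraction of missing information for each PCL-5 estimate (2 and 4 months), together with the number of observed values, so that a reader can judge the remaining Monte Carlo error.
- As a minor addition, state which df were used in pooling. If a small-sample adjustment is used, give the complete-data df: 49 for a paired comparison of all 50 participants, or the residual df for a regression.

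The cost is seconds of computing and a sentence or two of text. Section 6 is written in the past tense, but this is no obstacle: re-imputing and re-pooling need only the data already collected. If results from ten imputations exist, fix the seed before the re-run and report the new result whichever way it moves.
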